### 4.4 Sample size calculation

With 75 patients per arm, 96% power would be achieved to detect a difference of 5 points in STAI-S score between intervention and control, with a mixed model analysis of repeated measures, at the two-sided 5% significance level in a design with 3 measurements per patient (baseline before surgery, at pre-operative holding and on day 1 post-operatively) having an autoregressive order 1 covariance structure when the standard deviation is 10 and the correlation between observations within the same patient is 0.6. The PASS software module for the test of two means in a repeated measures design was used for this calculation. Accounting for 5% drop-outs/non-compliant patients, 79 patients per arm (total 158) would be needed.

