##### *Baseline and surgery parameters*

- Age
- Length and weight
- American Society of Anesthesiologists classification (ASA class)
- Sociodemographic status (household, marital state, employment, education)
- Intoxications
- History of sedative or anti-depressive medication use
- Type of breast cancer and type of breast cancer surgery
- Underlying disease(s)

*Intraoperative*

- The following vital signs are scored at baseline (e.g. measured on the outpatient department), at arrival on the operation room, just before induction and at the first measurement after induction:
  - Systolic-, diastolic-, and mean blood pressure (mmHg)
  - Heart rate (beats per minute)
  - Oxygen saturation (SpO2 in %)
  - Respiratory rate (breaths per minute)
- Type and dose of anesthetic medication used for induction of anesthesia
- Type and dose of vasoactive medication used during or within five minutes after induction
- Anesthetic medication used for maintenance of anesthesia
- Type and dose of administered opioids
- Type and dose of other analgesia
- Anti-emetics used
- Perioperative anesthesiological management regarding locoregional techniques
- Duration of anesthesia
- Duration of surgery

*Postoperative - recovery room*

- Vital signs
- Highest NRS during admission in the recovery room
- Mean cumulative intravenous opioid dose administered during admission in the recovery room (MEQ)
- Postoperative nausea or vomiting (Y/N)

**8.2 Randomisation, blinding and treatment allocation***Randomisation*

Patients will be randomly allocated to the study arms (usual care or Slow PACE breathing) using blocked randomization with age (<50 versus ≥50) as randomisation stratification factor in Castor.

*Blinding*

In this trial it is not possible to blind the patient or the investigators.

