### 10.3 Primary study parameter

For analyzing the STAI-S, a mixed model for repeated measures data (T1= pre-operative, and T2= post-operative) will be used to test for differences between study arms, adjusted for STAI-S at baseline and randomization stratification factor age group. Akaike's information criteria (corrected) and Bayesian information criteria will be used for choosing the correlation structure. Diagnostic residual plots will be used to inspect model assumptions. In a separate exploratory analysis, STAI-T at baseline (dichotomized for anxiety status with cut-off 40 (see protocol Section 8.3.2) will be added as an explanatory variable in the regression, with and without interaction with study arm. The same will be done with HADS-A at baseline, dichotomized using cut-off 8 (Section 8.3.2).

Additional analyses will be performed on the primary study parameter: Differences in STAI-S between measurements T0 and T1, between T1 and T2 and between T0 and T2 will be compared between study arms using linear regression models for each comparison, adjusting for baseline measurements.

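### Section 10.3 takes the separate T1 and T2 effects from change-score regressions that do not name the age stratum and can use only patients with both scores; the effect is small, and the planned mixed model can supply these estimates better

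*Combined protocol and SAP*

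**What the plan says.** Section 10.3 fits a mixed model to STAI-S at T1 and T2, "adjusted for STAI-S at baseline and randomization stratification factor age group". It names no arm-by-visit term and no contrast at a single visit. The additional analyses in the same section take the differences T0 to T1, T1 to T2 and T0 to T2, which "will be compared between study arms using linear regression models for each comparison, adjusting for baseline measurements".

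Section 8.2 allocates patients "using blocked randomization with age (<50 versus ≥50) as randomisation stratification factor in Castor".

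Section 10.2 promises intention-to-treat analysis of all randomised patients. No section gives a rule for missing scores. The only figure for loss is in Section 4.4: "Accounting for 5% drop-outs/non-compliant patients, 79 patients per arm (total 158) would be needed".

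**The concern.** A change from T0, adjusted for T0, is the adjusted arm difference at the later visit. The change-score regressions are therefore the plan's only source for the effect at T1 and the effect at T2. Those two effects mean different things. By Sections 4.4 and 8.3.2, T1 is completed before surgery, in the holding area. By Section 8.3.3, breathing at induction starts after the time-out in the operating room. A T1 effect thus reflects the training and home practice, and only T2 follows the whole intervention. Readers will use the split to interpret the overall result.

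As written, the split comes from a different covariate set and a different set of patients than the primary result. A patient with T1 but no T2 counts in the mixed model and drops out of the T0-to-T2 regression, although her T1 score carries information about T2. If missing T2 depends on T1, the regression estimate is biased. T2 is the likelier visit for loss: T1 is collected on a device handed over by the investigator, T2 through an online form after surgery.

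**Working it through.** **Inputs.** Section 4.4 gives "With 75 patients per arm, 96% power would be achieved to detect a difference of 5 points in STAI-S score", "at the two-sided 5% significance level in a design with 3 measurements per patient", "having an autoregressive order 1 covariance structure when the standard deviation is 10 and the correlation between observations within the same patient is 0.6", and 79 per arm after 5% loss. The documents give no missing rate per visit, no missingness mechanism, no age effect and no age split. All of these are assumptions below.

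**1. The plan's own figure.** The variance of the mean of three AR(1) scores is 100 × (3 + 2 × (0.6 + 0.6 + 0.36)) / 9 = 68.0. With 75 per arm the standard error is √(2 × 68 / 75) = 1.347, and 5 / 1.347 − 1.96 = 1.75, which gives 96.0% power. 75 / 0.95 = 78.9, so 79 per arm. Both figures reproduce.

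**2. What the change regressions estimate.** T1 − T0 = a + b·arm + c·T0 + e is the same equation as T1 = a + b·arm + (c + 1)·T0 + e. The arm coefficient b is identical, and a numerical check agreed. The same holds for T2.

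**3. Precision at T2.** Given T0:
- variance of T1 = 100 × (1 − 0.6²) = 64
- variance of T2 = 100 × (1 − 0.36²) = 87.04
- covariance = 100 × (0.6 − 0.6 × 0.36) = 38.4
- residual correlation r = 38.4 / √(64 × 87.04) = 0.514, so r² = 0.265

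Let a fraction m lack T2, with n = 79 per arm. The regression variance is 2 × 87.04 / (n(1 − m)). The variance from a mixed model with an arm-by-visit term is 2 × 87.04 × [r²/n + (1 − r²)/(n(1 − m))].

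| m | SE, regression | SE, mixed model | Power for 5 points |
|---|---|---|---|
| 5% | 1.523 | 1.513 | 90.7% vs 91.1% |
| 10% | 1.565 | 1.544 | 89.2% vs 89.9% |
| 20% | 1.660 | 1.615 | 85.4% vs 87.2% |
| 30% | 1.774 | 1.702 | 80.5% vs 83.6% |

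At 5% the gain is 1 − 1.513/1.523 = 0.7%, about one effective patient per arm (75.0 vs 76.1). The share of the added variance that is recovered is r², about a quarter.

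**4. Bias at T2.** Simulations used the plan's SD and correlation, a true effect of −5, and missing T2 that depends on T1 in the same way in both arms.
- 5% missing: the regression gives −4.91 if the odds of missing rise 2.7-fold per 10 STAI-S points, and −4.85 if they rise 4.5-fold. Across checks the bias was about 0.05 to 0.15 points.
- 25% and 29% missing: the regression gives −4.74 and −4.55, a bias of about 0.25 to 0.5 points.
- If only the intervention arm's missingness depends on T1 (2.7-fold odds) and the control arm's is random, the sign reverses: −5.2, −5.4 and −5.7 at 5%, 10% and 20% missing. The likelihood estimate using T1 stays near −5.0.

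**5. Age group.** Assume 30% of patients are under 50 and the age groups differ by a points. This adds v = a² × 0.3 × 0.7 to the variance if age is left out: 1.89 for 3 points, 5.25 for 5 points.
- Age shifts T0, T1 and T2 equally: residual T1 variance = (100 + v) − (60 + v)²/(100 + v) = 64.30 or 64.80 against 64. The standard error is 0.2% or 0.6% wider.
- The age difference remains in full after baseline adjustment: √((64 + v)/64) gives 1.5% or 4.0% wider.

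**6. Which mixed model is needed.** Under the plan's AR(1) inputs the slope on T0 is 0.6 at T1 and 0.36 at T2. With an arm-by-visit term but one common baseline slope, the T2 estimate was −5.07 at 25% missing and −5.15 at 29%. With a baseline-by-visit term but equal variances at the two visits it was −4.92 at 27%. Baseline-by-visit with an unstructured covariance restored about −5.0.

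**The case against.** The strongest reply is that these are additional analyses. No confirmatory conclusion rests on them, baseline-adjusted regression at each visit is standard practice, and the primary model already includes age group and both visits. That stands, and it is why the point is minor.

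The 5% allowance in Section 4.4 also covers non-compliant patients, who may still return a T2 form. Missing rates of 25% to 30% are therefore well outside the plan's expectation. That stands too: at 5% the bias is a small fraction of a standard error of about 1.5.

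The phrase about baseline measurements might be meant to include age group. This is less convincing, because the primary-model sentence in the same section lists baseline STAI-S and age group separately. Still, the phrase is loose enough that the plan can only be said not to name age.

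Two further limits are fair. Dropping incomplete patients is inferred from the method, since no missing-data rule is written. And a reader might infer that the mixed model gives the visit effects with no loss. It does not: about a quarter of the lost information on T2 is recovered, a patient without T0 or without both later scores is not recovered at all, and the model as now written has no arm-by-visit term.

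**Conclusion.** The point holds as a minor one. The only visit-specific estimates in the plan come from regressions that do not name the randomisation stratum and need both scores, so they need not agree with the primary model in covariates or patients.

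At 5% loss the cost is about 0.05 to 0.15 points of bias at T2, if missingness depends on T1 alike in both arms, and under 1% in precision. It grows to about 0.25 to 0.5 points if 25% to 30% of T2 forms are missing. The direction depends on the mechanism, which the documents do not give. Leaving out age makes the T1 standard error 0.2% to 0.6% too wide if age shifts all scores equally. The 4% figure needs a 5-point age difference that baseline STAI-S does not absorb.

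A reader might infer that the primary result, its power or the intention-to-treat principle is compromised. The documents do not support that: the primary model includes age group and can use a patient with either later score, and the 96% power and 79 per arm reproduce. Nor do they support calling the intervals materially too wide, since no age effect is stated and the error is conservative.

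**What to change.** In Section 10.3, specify arm-by-visit and baseline-by-visit terms in the primary mixed model, with an unstructured 2 × 2 covariance for T1 and T2 in place of selection by information criteria, and keep age group. Report the arm contrasts at T1, at T2 and for T2 minus T1 from this model, using every patient with T0 and at least one later score. State the missing-at-random assumption. Say in the same sentence which single arm contrast is the primary test, so that the added terms do not leave it open.

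If the change-score regressions are kept as supportive analyses, add age group to them and state which patients they include.

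The cost is a few sentences of SAP text. No data, patients or visits are added, and the sample size stays as planned.

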### **10.5 Other study parameters**

Demographic data, baseline vital signs, NRS scores, perioperative administered cumulative drugs dosage, applied loco-regional techniques and duration of anesthesia will be reported.

### **10.6 Interim analysis**

No planned interim analysis will be performed

## 11. ETHICAL CONSIDERATIONS

### 11.1 Regulation statement

The study will be conducted according to the principles of the Declaration of Helsinki (7th version of Fortaleza, Brazil, October 2013) and in accordance with the Medical Research Involving Human Subjects Act (WMO) and comply with Good Clinical Practice (GCP) Guidelines and all applicable national regulatory requirements and general data protection regulations (GDPR).

### 11.2 Recruitment and consent

#### 11.2.1 Recruitment

Patients will be screened for eligibility during the routine preoperative consultation. Should a patient be eligible, then she will be contacted by one of the researchers by phone to receive oral information about the study. This contact will take place at least 2 weeks prior to the surgical procedure.

Many patients in this population live far from the hospital and do not frequently visit the Antoni van Leeuwenhoek hospital in person. If receiving neoadjuvant treatment, they often receive this in a hospital near their home address. To benefit patient comfort and because our easy-to-learn intervention is very low risk and low burden, we aim to provide all contact for this study online, supported by additional contact by (video)phone. We used the 'Handreiking elektronische toestemmingsverlening voor deelname aan medisch-wetenschappelijk onderzoek, 22 augustus 2022' and the 'Checklist METC NedMec eConsent (NL) version 1 jan 2023' provided by the Centrale Commissie Mensgebonden Onderzoek (CCMO) to ensure compliance with article 6 lid 2 WMO.

If a patient is interested in participation, the document with the patient information and informed consent form will be sent digitally in an attachment by email using Zivver. Zivver is a service used in the AvL to send and receive information securely between patients and doctors in end-to-end encrypted emails protected by a personal password. Only the sender and the recipient can open the email and access the attached files. Zivver nor the IT department has access to the personal password, nor to the decryption key. This means that nobody but the sender and the recipient of the message can decrypt the message and read its content. Zivver complies with the concerning privacy and information protection regulations, like GDPR.

In Zivver the researcher can audit if the email has been received and opened by the recipient. The IT department has access to the audit-logs in which they can audit when

and where the email has been accessed and if any settings have been changed, without having access to the content of the email.

### **11.2.2 Consent**

The patients will be given sufficient time, at least 48 hours, to consider their decision and discuss this with their relatives or the independent expert. If the patient is willing to participate, oral consent is obtained by telephone. Hereafter an email with the patient information and informed consent form (IFC), signed and dated by the researcher, will be sent as attachment using Zivver to the email address that the participant personally gives to the researcher during this telephone contact. This email is secured twice with a personal password which the researcher will give to the participant during the same phone call. The participant will sign and date the IFC and send it back as attachment to the researcher by email using Zivver. The participant will thus have a digital copy of the IFC. If the patient prefers to give written consent personally, then an appointment with one of the researchers will be made in the hospital to obtain written informed consent and for further personal contact and information.

The IFC signed by both participant and researcher will be stored digitally and will be safeguarded by the primary investigator digitally and protected by a password (also see §12.1).

### **11.3 Objection by minors or incapacitated subjects**

Not applicable.

### **11.4 Benefits and risks assessment, group relatedness**

The patient risk is negligible. The patient burden comprises of the training instruction, daily practice and completing the questionnaires is considered minimal.

### **11.5 Compensation for injury**

The sponsor/investigator has been granted a dispensation of the liability insurance by the accredited METC.

### **11.6 Incentives**

As this is an investigator initiated study, without additional funds, no financial incentive is available for patients. The patients in the intervention group are trained a stress reducing breathing technique, which they can apply in other stressful situations. The control group will have access to the training video and audio fragments on request, after the study has finished.

## **12. ADMINISTRATIVE ASPECTS, MONITORING AND PUBLICATION**

### **12.1 Handling and storage of data and documents**

All data will be handled confidentially and anonymously. Every subject will receive a subject identification code that contains no patient identifying data. The code list and key to the code will be safeguarded by the primary investigator digitally and protected by a password. Should other parties, such as a monitor or the Inspectie Gezondheidszorg en Jeugd, require data to be traced back to an individual subject, this code list can be used. All involved parties will handle patient data in a confidential manner. All relevant data will be recorded and stored in an electronic case report form (eCRF) using this identification code. Castor will be used to minimize errors and to ensure traceability. The data will be recorded in the eCRF at the bedside, or they will be extracted from the electronic patient record. All signed digital informed consent forms will be stored digitally, safeguarded by the primary investigator and protected by a password. The local researchers and project leader are responsible for data processing and are the only people that have access to the source data. All data will be stored for the length of the study and for 15 years afterwards, for further publication. All handling of personal data will comply with the Dutch Personal Data Protection Act.

### **12.2 Monitoring and Quality Assurance**

As this trial is a low risk trial, we protocolize for a planned monitoring once a year.

### **12.3 Amendments**

Amendments are changes made to the research after a favorable opinion by the accredited METC has been given. All amendments will be notified to the METC that gave a favorable opinion.

Non-substantial amendments will not be notified to the accredited METC and the competent authority but will be recorded and filed by the sponsor.

### **12.4 Annual progress report**

The sponsor/investigator will submit a summary of the progress of the trial to the accredited METC once a year. Information will be provided on the date of inclusion of the first subject, numbers of subjects included and numbers of subjects that have completed the trial, serious adverse events/ serious adverse reactions, other problems, and amendments.

### **12.5 Temporary halt and (prematurely) end of study report**

The investigator/sponsor will notify the accredited METC of the end of the study within a period of 8 weeks. The end of the study is defined as the last patient's last visit.

The sponsor will notify the METC immediately of a temporary halt of the study, including the reason of such an action.

In case the study is ended prematurely, the sponsor will notify the accredited METC within 15 days, including the reasons for the premature termination.

Within one year after the end of the study, the investigator/sponsor will submit a final study report with the results of the study, including any publications/abstracts of the study, to the accredited METC.

### **12.6 Public disclosure and publication policy**

This study has been registered with the Netherlands Trial Register under the trial number NL84554.041.23. The results of the study will be published in a peer-reviewed (inter-) national scientific journal. We will submit analyses to scientific journals in the field of anesthesiology. The results of this study will be disclosed unreservedly according to the Central Committee on Research Involving Human Subjects (CCMO) statement on publication policy (<http://www.ccmo.nl/attachments/files/ccmo-statement-publicatiebeleid-3-02-en.pdf>). Data will be made accessible according to the FAIR guidelines.

## **13. STRUCTURED RISK ANALYSIS**

Not applicable.

